6.2.2.6. Overall Survival

Overall survival (OS) is defined as the time from 'start date' to the date of death due to any cause. Patients last known to be alive will be censored at date of last contact.

$$\text{OS (months)} = [\text{date of death or censoring} - \text{'start date'} + 1] / 30.4375.$$

Kaplan-Meier estimates (product-limit estimates) will be presented by treatment group together with a summary of associated statistics including the median OS time with 2-sided 95% CIs. In particular, the OS rate at 3, 6, 9, 12, 15, and 18 months will be estimated with corresponding 2-sided 95% CIs. The CIs for the median will be calculated according to Brookmeyer and Crowley and the CIs for the survival function estimates at the time points defined above will be derived using the log-log transformation according to Kalbfleisch and Prentice (conftype=loglog default option in SAS Proc LIFETEST) with back transformation to a CI on the untransformed scale. The estimate of the standard error will be computed using Greenwood's formula.

Frequency (number and percentage) of patients with an event (death) and censoring reasons will be presented by treatment group. Reasons for censoring will be summarized according to the categories in Table 5 following the hierarchy shown.

Table 5. OS Censoring Reasons and Hierarchy

Hierarchy	Condition	Censoring Reason
1	No event and [End of study (EOS) = Subject refused further follow-up]	Subject refused further follow-up
2	No event and [lost to follow-up in any disposition page OR data cut-off date – last contact date > 16 weeks]	Lost to follow-up
3	No event and none of the conditions in the prior hierarchy are met	Alive

The OS time or censoring time and the reasons for censoring will also be presented in a patient listing.

Time of Follow-Up for OS

A Kaplan-Meier plot for OS follow-up duration will also be generated to assess the follow-up time in the treatment groups reversing the OS censoring and event indicators.

6.2.3. Pharmacokinetic Endpoints

6.2.3.1. Non-compartmental Analysis

Standard pharmacokinetic parameters (eg, C_{trough} , C_{max} , T_{max} , $t_{1/2}$, AUC_{0-last} , $AUC_{0-\infty}$, AUC_{tau} , CL , V_{ss} and Rac) will be estimated using non-compartmental methods. Pharmacokinetic parameters for PF-05082566 and rituximab will be evaluated.

Descriptive statistics (n, mean, SD, %CV, median, minimum, maximum, geometric mean, its associated 95% CI and geometric %CV) of serum concentrations for PF-05082566 and rituximab will be presented in tabular form by study day, cycle, dose and nominal time. Concentrations with zero values will be excluded from the calculation of geometric means, its associated 95% CI and geometric %CV. Linear and semi-log plots of median serum concentrations vs nominal time will be prepared by study day, cycle and dose. Similar plots will be prepared for each individual patient's serum concentrations.

Pharmacokinetic parameters will be listed and summarized by cycle and dose using descriptive statistics (n, mean, SD, %CV, median, minimum, maximum, and geometric mean, its associated 95% CI and geometric %CV). Dose-normalized parameters (eg, C_{trough} , C_{max} and AUC) will also be listed and summarized. Pharmacokinetic parameters with zero values will be excluded from the calculation of geometric means, its associated 95% CI and geometric %CV.

$AUC_{0-\infty}$ (AUC_{τ} at steady state), AUC_{0-last} and C_{max} for PF-05082566 may be plotted against dose (using a logarithmic scale). These plots will include individual patient values and the geometric means for each dose. These plots will be used to help understand the dose proportionality for PF-05082566.

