3.1.1. Portion A Expansion Cohorts

As of September 2016, 34 patients with advanced solid tumor, including 20 patients with melanoma, who had documented disease progression per RECIST v1.1 on a previous immune checkpoint inhibitor therapy (see [Section 4.1](#) for the definition of disease that progressed from previous immune checkpoint inhibitor therapy) have been enrolled in the expansion cohorts of Portion A and treated at the 0.24 or 1.2 mg/kg dose levels of PF-05082566. These two dose levels will be further expanded and an intermediate dose level (0.6 mg/kg) will also be evaluated. Approximately 40 additional patients with melanoma who had documented disease progression per RECIST v1.1 on a previous immune checkpoint inhibitor therapy will be randomized 2:1:1 to treatment with single agent PF-05082566 at the 0.6, 0.24, or 1.2 mg/kg dose levels. The study design of the Portion A expansion cohorts is illustrated in Figure 3.

Figure 3. Study Design of the Expansion Cohort of Portion A

[figure not shown]

For each cohort the primary diagnosis, the PF-05082566 dose levels (0.24, 0.6, or 1.2 mg/kg), the PF-05082566 drug preparation to be used (10 mg/mL or 25 mg/mL) and the enrollment status are illustrated. No switch between the 2 different preparations is allowed during study treatment.

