5.3. Investigational Product Supplies

5.3.1. Dosage Form(s) and Packaging

5.3.1.1. PF-05082566

PF-05082566 drug product will be supplied by the sponsor or designee. PF-05082566 drug product is a solution and should be stored refrigerated at 2-8°C. PF-05082566 drug product will be supplied in glass vials at a 10 mg/mL (100 mg/vial) and 25 mg/mL (125 mg/vial) concentration and labeled as open supplies. Each vial is packed in an individual carton. For packaging and labeling information on rituximab, refer to the most recent version of the local product labeling. The administration of each preparation in the Portion A and Portion B expansion cohorts should follow [Table 10](#) below; see [Section 3.1](#) for additional details about the different expansion cohorts. **No switch between the 2 different preparations is allowed during study treatment.** See the IP manual for additional information.

Table 10. PF-05082566 Preparations to be Administered in the Expansion Cohorts

Portion	Cohort	PF-05082566 dose level	Preparation to Use	
			10 mg/mL (100 mg/vial)	25 mg/mL (125 mg/vial)
A Non Randomized	CCI			
	Other Histology	1.2 or 0.24 mg/kg	X	
A Randomized	Melanoma	1.2 mg/kg		X
	Melanoma	0.6 mg/kg		X
	Melanoma	0.24 mg/kg		X
B	FL-1	1.2 mg/kg	X	
	FL-2	0.24 mg/kg	X	
	FL-3	1.2 mg/kg or 0.24 mg/kg		X
	DLBCL	1.2 mg/kg	X	

Grey Shading: close to enrollment; No shading: Open to enrollment. No switch between the 2 different preparations is allowed during study treatment.

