5. GENERAL METHODOLOGY AND CONVENTIONS

5.1. Hypotheses and Decision Rules

5.1.1. Hypotheses and Sample Size Determination

No formal statistical hypothesis testing is planned.

The sample sizes planned for the study arise from logistic feasibility and past experience with First in Human (FIH) studies in oncology and are not driven by statistical considerations. It is expected that approximately 277 patients will need to be enrolled to achieve the objectives of the study.

Due to the dynamic nature of the Bayesian allocation procedure, the sample size of the TITE-CRM approach cannot be determined in advance. The maximum sample size is set as 45 in order to have a reliable and accurate estimate of the MTD based on simulation results. Based on probability theory, a sample size of 45 will ensure the estimates of any binary variable (eg, objective response rate) have a 95% confidence interval (CI) of width <0.30 . A sample size of 45 also enables detection of any unexpected toxicity that occurs at 5% rate (in a non-dose-dependent fashion) with a probability of 0.90, and that occurs at 10% rate with a probability of 0.99.

A stopping rule will also be implemented if:

- Maximum sample size ($N=45$) is reached; or
- 9 DLT-evaluable patients have been treated at the estimated MTD; or
- all doses appear to be overly toxic and the MTD cannot be determined in the current trial.

Portion A expansion cohorts include patients with solid tumors of interest who progressed after treatment with an immune checkpoint inhibitor (anti-CTLA-4, anti-PD-1/PD-L1). The target sample size is approximately 20 patients with advanced melanoma at each tested dose (0.24 mg/kg, 0.6 mg/kg, 1.2 mg/kg) and approximately 20 patients, including other tumor types. With 20 patients with advanced melanoma, the maximum standard error of the ORR is 0.11.

Portion B expansion cohorts include approximately 80 patients with FL refractory to rituximab and to an alkylating agent at either 1.2 mg/kg or 0.24 mg/kg of PF-05082566. With 80 patients, the maximum standard error of the ORR is 0.06.

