6.2.4. Endpoints for Immunogenicity Data of PF-05082566 and Rituximab

ADA/ Nab data will be listed and summarized for PF-05082566 and rituximab by dose and for the entire study population. The percentage of patients with positive ADA and Nab will be summarized by dose and overall study population (eg. at baseline, post-dose, treatment-induced, treatment-boosted or anytime of the study). For patients with positive ADA, the magnitude (titer), time of onset, and duration of ADA response will also be described, if data permit. The impact of ADA/Nab on PK, safety/efficacy will also be assessed, if data permit.

CCI
[Redacted text block containing multiple paragraphs of blacked-out content]

C [Redacted]
C [Redacted]
I [Redacted]

I [Redacted]

I [Redacted]

I [Redacted]

[Redacted]

[Redacted]

[Redacted]

CCI [Redacted]

[Redacted]

[Redacted]

[Redacted]

CCI [REDACTED]

[REDACTED]	[REDACTED]	[REDACTED]
[REDACTED]	[REDACTED]	[REDACTED]
[REDACTED]	[REDACTED]	[REDACTED]
[REDACTED]	[REDACTED]	[REDACTED]
[REDACTED]	[REDACTED]	[REDACTED]
[REDACTED]	[REDACTED]	[REDACTED]
[REDACTED]	[REDACTED]	[REDACTED]
[REDACTED]	[REDACTED]	[REDACTED]

[REDACTED]
[REDACTED]
[REDACTED]

[REDACTED]

[REDACTED]

[REDACTED]

CCI [REDACTED]

[REDACTED]

[REDACTED]

CCI

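### ORR, PK and ADA tables pool the randomised melanoma patients with earlier non-randomised patients at the same dose, and no visible table isolates the randomised dose comparison or the two preparations

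*SAP*

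**What the plan says.** **Grouping.** SAP sections 3.7.1 and 5.2 define a treatment group as a PF-05082566 dose, alone or with rituximab. Cohort, tumour type, preparation and method of allocation play no part. Section 6.2.2.1 gives ORR with a Clopper-Pearson interval by treatment group. Section 6.2.3.1 says "Pharmacokinetic parameters will be listed and summarized by cycle and dose using descriptive statistics", and section 6.2.4 says "ADA/ Nab data will be listed and summarized for PF-05082566 and rituximab by dose and for the entire study population". Section 6.4 plans no subset analyses.

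**Cohorts.** Protocol section 3.1.1 reports that "34 patients with advanced solid tumor, including 20 patients with melanoma" were already enrolled by September 2016 at 0.24 or 1.2 mg/kg. "Approximately 40 additional patients with melanoma" "will be randomized 2:1:1 to treatment with single agent PF-05082566 at the 0.6, 0.24, or 1.2 mg/kg dose levels". The SAP's sample-size target (section 5.1.1) is "approximately 20 patients with advanced melanoma at each tested dose (0.24 mg/kg, 0.6 mg/kg, 1.2 mg/kg").

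**Preparations.** Protocol section 5.3.1.1 states that "PF-05082566 drug product will be supplied in glass vials at a 10 mg/mL (100 mg/vial) and 25 mg/mL (125 mg/vial) concentration", and that "No switch between the 2 different preparations is allowed during study treatment". Table 10 there assigns 25 mg/mL to all three randomised melanoma arms and to FL-3, and 10 mg/mL to the other-histology, FL-1, FL-2 and DLBCL cohorts. One non-randomised Portion A row is redacted.

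**The concern.** The randomised cohort was added by Amendment 9 to support the choice of RP2D for the single agent, and Protocol section 3.6 bases that choice on the primary and secondary endpoints. Only the randomised patients give a dose comparison free of differences in enrolment period, allocation and preparation. The planned tables merge them with earlier patients, in proportions that differ by dose. A difference between earlier and later patients would then appear in the tables as a difference between doses.

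The merged patients are also counted under different rules. For randomised cohorts the FAS is everyone randomised and time runs from randomisation. For non-randomised cohorts it is everyone treated and time runs from first dose (SAP sections 2 and 4.1). A patient randomised but never treated is a non-responder; the earlier cohort has no counterpart.

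**Working it through.** **1. The plan's own precision.** Maximum SE = √(0.25/n). For n = 20 this is √0.0125 = 0.112 (SAP: 0.11). For n = 80 it is √0.003125 = 0.056 (SAP: 0.06). Both reproduce.

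**2. The target needs pooling.** 40 patients at 2:1:1 give 20 at 0.6, 10 at 0.24 and 10 at 1.2 mg/kg. About 20 melanoma patients at every dose is reached only by adding the 20 earlier ones: 10 + 10 at each outer dose, if they split evenly.

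**3. Effect on the melanoma ORR contrasts.** Let a earlier patients have received 0.24 and 20 − a received 1.2 mg/kg; the documents do not state a. Let delta be the ORR difference between earlier and randomised patients at the same dose. The spurious difference from 0.6 mg/kg is the earlier share times delta: a/(a + 10) at 0.24 and (20 − a)/(30 − a) at 1.2 mg/kg.

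| Earlier split, 0.24/1.2 | 0.6 v 0.24 | 0.6 v 1.2 | 0.24 v 1.2 |
|---|---|---|---|
| 10/10 | 10/20 = 0.50 × delta | 10/20 = 0.50 × delta | 0 |
| 5/15 | 5/15 = 0.33 × delta | 15/25 = 0.60 × delta | 0.27 × delta |
| 15/5 | 15/25 = 0.60 × delta | 5/15 = 0.33 × delta | 0.27 × delta |

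With an even split, an assumed delta of 10 points gives 5 spurious points and 20 gives 10. One response in a pooled group of 20 is 1/20 = 5 points.

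**4. Against sampling error, at ORR 20%.** The SE of a pooled 20 v 20 difference is √(0.16 × 2/20) = 0.126. Randomised only, it is √(0.16 × (1/20 + 1/10)) = 0.155 for 20 v 10, and √(0.16 × 2/10) = 0.179 for 10 v 10. For 0.6 v an outer dose with an even split, the pooled contrast has the larger mean squared error once 0.25 × delta² exceeds 0.024 − 0.016 = 0.008, that is, once delta exceeds √0.032 ≈ 0.18.

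**5. Portion B.** FL-1 (1.2 mg/kg) and FL-2 (0.24 mg/kg) both use 10 mg/mL. At planned numbers, FL-3 adds 60 patients on 25 mg/mL to one of these groups of 20. The FL expansion groups then stand at 60/80 = 75% on 25 mg/mL for the selected dose and 0/20 for the other. A preparation or era shift enters that final contrast at 0.75 × its size.

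**The case against.** The strongest reply has four parts.

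- **The 0.6 mg/kg row is not purely randomised.** 0.6 mg/kg was also an escalation level (Protocol section 3.3.1), and section 1.4 reports a responder there by June 2016. Read literally, the 0.6 mg/kg tables therefore include escalation patients. This stands: the claim that this group is all randomised and all on 25 mg/mL is true only of melanoma expansion patients. It does not rescue the tables, because adding escalation and other-histology patients makes each dose row more mixed.
- **Delta is hypothetical.** Nothing in the documents shows a preparation or era effect. It is the same antibody, dosed in mg/kg. This stands too, and a 5-point shift is small beside the interval of 5.7 to 43.7% for 4/20.
- **Pooling buys precision, and expanding the two existing doses was deliberate.** True. By step 4 the pooled contrast has the smaller mean squared error unless delta exceeds about 18 points. That argues for keeping the pooled row, not for showing it alone.
- **Nothing is formally tested, and listings and individual plots allow inspection by cohort.** These descriptive tables nevertheless feed the RP2D decision, and inspection after the event is not a planned comparison.

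Two further readings go too far. A reader might infer that the randomisation is ignored. In fact it sets FAS membership and classification, start date, efficacy baseline and disposition tables (SAP sections 2, 3.7.1, 4.1 and 6.5.2.1). A reader might also infer that the FL-3 dose choice is confounded with preparation. That choice rests on FL-1 and FL-2, which share one preparation; only enrolment period separates them, since FL-2 opens after FL-1 is assessed.

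**Conclusion.** The concern holds in this form: no visible efficacy, PK or ADA table uses the randomisation for a dose comparison or separates the two preparations. In melanoma, about half of any earlier-versus-randomised difference passes into each contrast with 0.6 mg/kg (0.33 to 0.60 for splits of 5/15 to 15/5). The contrast of 0.24 with 1.2 mg/kg is balanced if the earlier split was even, and otherwise carries up to 0.27 of it. In Portion B the mixing arises only in the final by-dose groups, and no planned table checks that exposure is the same across preparations.

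This rests on three things the documents do not give: the dose split of the 20 earlier melanoma patients, the size of delta, and those patients' preparation. The last is inferred to be the earlier one because they were enrolled by September 2016 and Amendment 9, which allowed a different preparation, is dated January 2017. If that inference fails, the era and allocation differences remain. Redacted SAP sections could not be checked.

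**What to change.** 1. **ORR.** Add a melanoma ORR table restricted to randomised patients, by assigned dose. Show it beside the pooled ORR, with the earlier cohort in its own row, and state that it is less precise: maximum SE is √(0.25/10) = 0.158 at n = 10, and 2/10 gives a 95% interval of 2.5 to 55.6%.
2. **PK and ADA/Nab.** Add descriptive PF-05082566 rows by preparation within dose, separately for single agent and combination, wherever both preparations were given. Intensive sampling is assured in only at least 5 patients per dose cohort (Protocol section 7.2.3.1), so AUC comparisons will be thin. Pre-dose and end-of-infusion samples in Cycles 1 to 4 are planned for all expansion patients and give a fuller check.

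No new patients or samples are needed. Table 10 fixes preparation by cohort, and the SAP already separates randomised from non-randomised cohorts for disposition. The cost is extra rows with wide intervals; the pooled rows stay.

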6.2.3.2. Population Pharmacokinetic Analysis

Pharmacokinetic and pharmacodynamic data from this study may be analyzed using modeling approaches and may also be pooled with data from other studies to investigate any association between PF-05082566 and rituximab exposure and CCI or significant safety/efficacy endpoints. The results of these analyses, if performed, may be reported separately.

6.2.4. Endpoints for Immunogenicity Data of PF-05082566 and Rituximab

ADA/ Nab data will be listed and summarized for PF-05082566 and rituximab by dose and for the entire study population. The percentage of patients with positive ADA and Nab will be summarized by dose and overall study population (eg. at baseline, post-dose, treatment-induced, treatment-boosted or anytime of the study). For patients with positive ADA, the magnitude (titer), time of onset, and duration of ADA response will also be described, if data permit. The impact of ADA/Nab on PK, safety/efficacy will also be assessed, if data permit.

CCI
[Redacted text block containing multiple paragraphs of blacked-out content]

C [Redacted]
C [Redacted]
I [Redacted]

I [Redacted]

I [Redacted]

I [Redacted]

[Redacted]

[Redacted]

[Redacted]

CCI [Redacted]

[Redacted]

[Redacted]

[Redacted]

CCI [REDACTED]

[REDACTED]	[REDACTED]	[REDACTED]
[REDACTED]	[REDACTED]	[REDACTED]
[REDACTED]	[REDACTED]	[REDACTED]
[REDACTED]	[REDACTED]	[REDACTED]
[REDACTED]	[REDACTED]	[REDACTED]
[REDACTED]	[REDACTED]	[REDACTED]
[REDACTED]	[REDACTED]	[REDACTED]
[REDACTED]	[REDACTED]	[REDACTED]

[REDACTED]
[REDACTED]
[REDACTED]

[REDACTED]

[REDACTED]

[REDACTED]

CCI [REDACTED]

[REDACTED]

[REDACTED]

CCI

6.4. Subset Analyses

The number of patients expected in each treatment group is small and therefore no subset analyses are planned in this study.

6.5. Baseline and Other Summaries and Analyses

6.5.1. Baseline Summaries

The following analyses will be based on the FAS overall and separately by treatment group.

6.5.1.1. Demographic Characteristics

Demographic characteristics and physical measurements will be summarized by treatment group using the following information from the ‘Screening/Baseline Visit’ eCRF pages.

- Demographic characteristics:
 - Gender: Male, Female.
 - Race: White, Black or African American, Asian, American Indian or Alaska Native, Native Hawaiian or other Pacific Islander, Other, Unknown.
 - Ethnic origin: Hispanic/Latino (Yes/No).
 - Age (years): summary statistics.
 - Age categories:
 - < 65 years, ≥ 65 years.
 - < 65, 65-<75, 75-<85, ≥ 85 years.

- Pooled Geographical Region (as applicable):
 - North America.
 - Europe.
 - Asia.
 - Rest of the World (Australasia, Latin America, Africa and/or Middle East will be included as additional pooled geographical regions if including >10% of the overall randomized population).
- Geographic Region (as applicable):
 - North America.
 - Latin America.
 - Western Europe.
 - Eastern Europe.
 - Middle East.
 - Australasia.
 - Asia.
 - Africa.
- Eastern Cooperative Oncology Group (ECOG) Performance Status: 0, 1, 2, 3, and 4.
- Physical measurements:
 - Height (cm).
 - Weight (kg).
 - Body Mass Index (BMI) (kg/m^2).
 - Body Surface Area (BSA) (m^2).

Site codes will be used for the determination of the patient's geographic region.

The listing of demographics and baseline characteristics will include the following information: patient identifier, treatment group, age, sex, race, ethnicity, height (cm), weight (kg), BMI (kg/m^2), BSA (m^2) and ECOG performance status.

6.5.1.2. Medical History

Medical history will be coded using the most current available version of Medical Dictionary for Regulatory Activities (MedDRA) and will be summarized from the ‘Medical History’ eCRF page. Medical history will be summarized as the numbers and percentages of patients by MedDRA preferred term (PT) as event category and MedDRA primary system organ class (SOC) as summary category. Each patient will be counted only once within each PT or SOC.

Medical history will be displayed in terms of frequency tables: ordered by primary SOC and PT in alphabetical order.

6.5.1.3. Disease Characteristics

Information on disease characteristics collected on ‘Primary Diagnosis’, RECIST, and IWGRC eCRF pages will be summarized overall and by treatment group. Summary statistics will be presented for the following.

From the ‘Primary Diagnosis’ eCRF page:

- Site of primary tumor;
- Primary diagnosis (summarize all categories collected in the ‘Primary Diagnosis’ eCRF page);
- Time since initial diagnosis to ‘start date’ (months), defined as (‘start date’ – date of initial diagnosis)/30.4375;
- For Portion A solid tumors: Time since diagnosis of local/regional recurrence of disease (months), defined as (‘start date’ – date of diagnosis of local/regional recurrence of disease)/30.4375.

From the RECIST tumor assessment eCRF page:

- Measurable disease (lesions) at baseline (Yes, No);
- Involved tumor sites at baseline.

From the IWGRC tumor assessment eCRF page:

- Involved tumor sites at baseline.

6.5.1.4. Prior Anti-cancer Therapies

The prior anti-cancer therapies are collected under the ‘Previous Systemic Therapy’, ‘Prior Radiation Therapy’ and ‘Prior Surgery’ eCRF pages.

The number and percentage of patients in each of the following anti-cancer therapy categories will be tabulated:

- Patients with at least one type of prior anti-cancer treatment;
- Patients with at least one prior anti-cancer drug therapy;
- Patients with at least one prior anti-cancer radiotherapy;
- Patients with at least one prior anti-cancer surgery;

Prior anti-cancer drug therapy will be summarized as follows based on the number and percentage of patients with the following:

- At least one prior anti-cancer drug therapy;
- Number of prior anti-cancer drug therapy regimens: missing / 1 / 2 / 3 / ≥ 4 ;
- Type of prior anti-cancer therapy;
- For Portion A solid tumors: Prior anti-cancer immune therapy (including PD-1, PD-L1, anti-CTLA4, others);
- Best response: Complete Response (CR) / Partial Response (PR) / Stable Disease (SD) / Progressive Disease (PD) / Unknown / Not applicable. Best response is derived from the last treatment regimen.
- For the expansion cohort patients:
 - Response to prior checkpoint inhibitor therapy (patients with melanoma in Portion A): Refractory / Relapsed, collected on the 'Subject Stratification' page.
 - Response to prior rituximab therapy (patients with FL in Portion B): Refractory / Relapsed, collected on the 'Subject Stratification' page.

The prior anti-cancer drugs will also be summarized based on the number and percentage of patients by the drug class and preferred term. A patient will be counted only once within a given drug class and within a given drug name, even if he/she received the same medication at different times. The summary will be sorted on decreasing frequency of drug class and decreasing frequency of drug name in a given drug class. In case of equal frequency regarding drug class (respectively drug name), alphabetical order will be used.

Prior anti-cancer treatments and procedures will be included in the listings that follow with a flag to identify prior therapies. These will include the patient identification number, and all the relevant collected data-fields on the corresponding eCRF pages.

- Listing of prior anti-cancer drug therapies;

- Listing of prior anti-cancer radiotherapy;
- Listing of prior anti-cancer surgeries.

